10.5 Laboratory Data

Quantitative chemistry and haematology parameters and fasting glucose values will be summarized descriptively at screening and discharge. Shift tables from screening with reference to normal ranges will be presented.

Serology and urinalysis results will only be listed.

Abnormal laboratory data will be flagged in the listings.

11 Other Analyses

No other analyses planned.

12 Changes in the Planned Analyses from Study Protocol

There are no changes to the protocol defined analysis.

13 Output

13.1 Software

SAS version 9.4 will be used to perform all the statistical analyses. PK analyses will be carried out using WNL Phoenix 8.1 or higher.

13.2 Reporting Conventions

13.2.1 Treatment, Visit and Subgroup Descriptors

In the tables, listings and figures, the treatments and the visits will be identified as described below.

Treatment group	Descriptor for treatment
CHF6001 800 µg/ 20 µg, 4 inhalations + [¹⁴ C]	CHF6001
CHF6001 IV Infusion 18.5 µg	

Output	Descriptor for visits
Tables	Screening, Day -1, Day 1, Day 2–10, Day 11, Follow-up
Listings	Same as above.
Figures	Same as ‘Tables’.

13.2.2 Decimal places

Quantitative variables except PK variables will be listed with the same number of decimal places as in the actual data.

In case of PK variables, plasma concentrations as well as calculated PK parameters will be presented with 3 decimal points except for t_{max} , t_{max_iv} , and t_{max_iv} which will be presented with 2 decimals. Values ≥ 1000 will be presented without the decimals and the whole number will be reported without roundings (i.e. 1237 is not rounded to 1240 and 12322 is not rounded to 12300).

The following rules on decimal places will be considered in the listings for the derived variables (in the analyses rounding will not be performed):

- BMI: whole numbers;
- average of triplicate measurements (ECG and Blood Pressure): same as the actual variable
- change from baseline: same as the variable considered.
- AE duration (days): whole number if duration (hours) ≥ 24 and 2 decimals in case of AE duration (hours) < 24 hours

The following rules on decimal places will be considered for the results of the analyses (if the analyses are performed on derived variables, the level of precision of the actual data is derived from the previous list):

- min, max: same as actual data;
- mean, SD, median, geometric mean: actual data + 1 decimal place;
- percentage, geometric CV%, CV%: 1 decimal place;

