4.3 Other Variables

No other variables defined.

5 Sample Size

According to the exploratory nature of the study, no formal sample size calculation was performed. A total of 8 subjects will be included in the study to characterize the absolute bioavailability and the mass balance of CHF6001.

6 Analysis Sets

The definitions of the analysis sets are summarised below. A final agreement on the subjects to be included in or excluded from each analysis set will be reached during the Data Review Meeting (DRM) before the database lock. Inclusions and exclusions from analysis sets will be fully documented in the Data Review Report (DRR).

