7.1 Statistical Significance

There is no hypothesis testing or confidence interval (CI) calculation performed hence statistical significance is not applicable.

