9.1 Pharmacokinetic Analysis

The concentration ratios of whole blood [^{14}C]-total and [^{14}C]-CHF6001 radioactivity to plasma [^{14}C]-total and [^{14}C]-CHF6001 radioactivity, individual and cumulative mass balance of [^{14}C]-total radioactivity (amount (Ae_u , cumulative Ae_u , Ae_f and cumulative Ae_u) and percentage of dose (fe_u , Fe_u , fe_f and Fe_f) recovered as [^{14}C]-total radioactivity in urine, feces and total excreta) will be calculated by radioanalysis laboratory (██████████).

In addition, metabolites in plasma accounting for $\geq 10\%$ of total radioactivity recovered in this matrix, structural characterization may be performed, where possible. For metabolites in urine and feces (total excreta) accounting for $\geq 10\%$ of total administered radioactivity, structural characterization may be performed, where possible.

If available, fraction of the relevant metabolites in plasma ($\text{Fr}_{\text{plasma}}$), fraction of the relevant metabolites recovered in urine and feces (Fr_{urine} , Fr_{feces} , $\text{Fr}_{\text{urine+feces}}$) will be reported in a separate report together with structural characterization performed by radioanalysis laboratory (██████████).

Urine and Feces [^{14}C]-CHF6001 and [^{14}C]-total radioactivity

Parameter	Units ^a	Definition
Ae_u	mg	amount excreted in urine (expressed in weight) over sampling interval
Cumulative Ae_u	mg	cumulative amount excreted in urine, calculated as the sum of the amount excreted in urine for each collection period
fe_u	%	percent of the dose excreted in urine over a sampling interval
Fe_u	%	cumulative percent of dose excreted in urine, calculated as the sum of the percent of dose excreted in urine for each collection period
Ae_f	mg	amount excreted in the feces over sampling interval
Cumulative Ae_f	mg	cumulative amount excreted in feces, calculated as the sum of the amount excreted in feces for each collection period
fe_f	%	percent of the dose excreted in feces over a sampling interval

Fe _f	%	cumulative percent of dose excreted in feces, calculated as the sum of the percent of dose excreted in feces for each collection period
CL _R	L/h	renal plasma clearance (urine [¹⁴ C]-CHF6001 only)
CL _{R_blood}	L/h	renal blood clearance where CL _{R_blood} = CL _R /R _{b/p} (urine [¹⁴ C]-CHF6001 only)

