14.1 Tables that need descriptive statistics

```
PROC UNIVARIATE DATA=dset NOPRINT;  
  VAR var1 var2 var3 ...varn;  
  BY byvar; (optional)  
  OUTPUT OUT=outname  
  N=n MEAN=mean MIN=min MAX=max MEDIAN=median STD=std CV=cv;  
RUN;
```

Notes:

- var1, var2 represent the variables for which summary statistics will be calculated;
- byvar represents by variables to be used if any
- out=outname specifies the output dataset that should be created

For tables that need also geometric mean and geometric CV, the original variable will be LOG transformed and the geometric mean will be calculated using exp (mean_Log_var) and Geometric CV will be calculated using $\sqrt{\exp[\text{std_Log_var}^2]-1}$

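### SAP 14.1 computes the geometric CV as a fraction, but SAP 13.2.2 reports it as a percentage to one decimal, so a true 30.7% would print as 0.3

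*SAP*

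**What the plan says.** **Geometric CV.** SAP 7.7 includes the geometric CV among the descriptive statistics for every PK variable except the t_max variables. SAP 14.1 gives the calculation. After a log transformation, "Geometric CV will be calculated using" the square root of exp(s²) − 1, where s is the SD of the logged variable. There is no multiplication by 100. The display rule in SAP 13.2.2 reads "percentage, geometric CV%, CV%: 1 decimal place". SAP 9.8 also refers to the CV of the geometric mean with a percent sign. The arithmetic CV in the same tables comes from the SAS output line "MEAN=mean MIN=min MAX=max MEDIAN=median STD=std CV=cv".

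**Amounts excreted.** The urine and feces table in SAP 9.1 defines Ae_u as "amount excreted in urine (expressed in weight) over sampling interval" and gives its unit as mg. Ae_f and the cumulative amounts are also in mg. A footnote lets units follow the bioanalytical laboratory, a preferred presentation unit, or the dose units. SAP 9.1 also says that the analysis uses the actual dose in mg. SAP 13.2.2 states that "calculated PK parameters will be presented with 3 decimal points". Minimum and maximum keep the precision of the data; mean, SD, median and geometric mean get one decimal more. The IV dose is 18.5 µg (SAP section 2; protocol 6.2.1).

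**Inference.** SAP 7.1 states: "There is no hypothesis testing or confidence interval (CI) calculation performed hence statistical significance is not applicable".

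**The concern.** The formula and the display rule for the geometric CV are on different scales. One decimal suits a percentage; applied to a fraction, it leaves one significant digit at most. The study is purely descriptive, with 8 subjects and no confidence intervals, so the geometric CV is the measure of spread that goes with the geometric mean of F_inh and of the exposure parameters. A value of 0.3 under a percent heading could be read as 0.3% variability. Even a reader who guesses the scale recovers the value only to within about 5 percentage points.

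The amounts raise a similar but smaller question: whether three decimals of a milligram can show parts of a 0.0185 mg dose.

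**Working it through.** **Dose, the ceiling for any amount excreted.** The protocol's study plan gives 10 mL at 1.85 µg/mL: 10 × 1.85 = 18.5 µg = 0.0185 mg. This reproduces the stated dose.

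**Geometric CV.** The documents give no expected variability, so the log-SD s is assumed over a range. Formula as in SAP 14.1: g = sqrt(exp(s²) − 1). Example: s = 0.30 gives sqrt(exp(0.09) − 1) = 0.3069.

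| Assumed s | g | Printed as the SAP stands | 100 × g, one decimal |
|---|---|---|---|
| 0.20 | 0.2020 | 0.2 | 20.2% |
| 0.25 | 0.2540 | 0.3 | 25.4% |
| 0.30 | 0.3069 | 0.3 | 30.7% |
| 0.40 | 0.4165 | 0.4 | 41.7% |
| 0.50 | 0.5329 | 0.5 | 53.3% |

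A fraction prints as 0.3 when it lies from 0.25 to just under 0.35, that is, a true CV of about 25% to 35%. It prints as 0.0 below 0.05, that is, below 5%.

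**Amounts excreted, if mg is kept.**
- Individual values, minimum and maximum (three decimals): printed as 0.000 below 0.0005 mg, and 0.0005 / 0.0185 = 2.7% of dose. One display step is 0.001 / 0.0185 = 5.4% of dose.
- Mean, SD, median and geometric mean (four decimals): printed as zero below 0.00005 / 0.0185 = 0.27% of dose. One step is 0.0001 / 0.0185 = 0.54%.
- Illustration: 13 post-dose urine intervals at 2.6% of dose each total 13 × 2.6 = 33.8%. Each is 0.026 × 0.0185 = 0.00048 mg and would be listed as 0.000.
- In µg to three decimals, 1%, 5% and 50% of dose print as 0.185, 0.925 and 9.250. In mg they print as 0.000, 0.001 and 0.009.

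**Effect on estimates.** SAP 13.2.2 says that derived variables are not rounded in the analyses. F_inh, CL_R, Fe and Fe_met are therefore computed from unrounded values.

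**The case against.** **On the geometric CV.** The percent sign in SAP 13.2.2 and 9.8 shows that a percentage was meant, and a programmer may well add the factor. SAP 13.4 requires independent second programming, comparison with the shells and checks between related outputs. The arithmetic CV, SD and range stand in the same table, and all individual parameters are listed, so a reader could recompute the geometric CV for 8 subjects.

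Most of this stands as mitigation, but it does not remove the mismatch. Two programmers who both follow SAP 14.1 will agree with each other, so a comparison of their outputs need not reveal the error. The check against shells and related outputs might. The contrast with the arithmetic CV assumes that SAS returns that statistic in percent, which the SAP does not state; the conflict between formula and label does not depend on it.

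**On the amounts.** The case against is stronger here. The footnote permits other units. Ae is not among the variables named for summary in protocol 12.3.4 or SAP 4.1; Fe is. Recovery in percent of dose carries the mass-balance result. The table shells were not in the text available for review, so the final units and headings cannot be seen. What remains is that mg is the listed unit, that SAP 9.1 also uses mg for the dose, and that individual listings would be coarse if mg were kept.

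**Stronger readings.** A reader might infer that the Ae tables would consist mostly of zeros, or that 2.7% of dose is the threshold for every output. The documents do not support either: summary means and medians have a fourth decimal, and an interval with 5% of dose prints as 0.001. A reader might also infer that a printed zero could not be told from a missing or BLQ result, because SAP 9.6 sets those to zero when Ae is calculated. SAP 9.8 provides flags in the applicable listings, which answers part of this.

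**Conclusion.** The geometric CV point holds on the SAP's own text: the formula gives a fraction, and the output rule calls for a percentage to one decimal. As written, the reported value is 100-fold too small for its label and keeps at most one significant digit over the range of variability tried above. That range is assumed; the mismatch itself rests on no assumption.

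The amounts point is secondary and conditional. It applies only if mg is retained, and then only to individual values and to minimum and maximum, which print as 0.000 below 2.7% of the dose.

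Neither point supports a claim that bioavailability or mass balance would be wrongly estimated, or that the information would be lost for good. Both are minor specification faults in how results are reported.

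**What to change.** In SAP 14.1, write geometric CV% = 100 × sqrt(exp(s²) − 1), with s the SD of the log-transformed variable. The one-decimal rule in SAP 13.2.2 can then stay.

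In SAP 9.1, use the latitude in the units footnote to present Ae and cumulative Ae in µg or ng. The current decimal rule then works unchanged.

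The cost is two short text edits. Design, conduct and calculations are not affected.

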13.2.3 Other reporting conventions

Unless otherwise stated, listings will be sorted by Subject ID.

In a listing, in the case that a subject's record has been continued to the next page, an appropriate identification (e.g., the subject ID number) must be presented at the beginning of that page.

In general, dates will be presented on listings in the format ddmmmyyyy (date9.) and time in the format hh:mm (time5.). In case of partial dates or times, missing information will be replaced by dashes.

13.3 Format

In the top left portion of each table/listing, a table/listing number followed by the title of the table/listing will be presented. After the title line, optional sub-title or analysis set information can be presented. Horizontal lines will appear before and after the column heading of the table/listing. Footnotes will be put under the main body of text at the bottom of the page.

The sponsor name, protocol number, programmer's User ID, status of the table/listing (i.e. draft or final) and SAS program name will appear bottom left in a string and the page number will appear on the bottom right corner of each table/listing. The date and time of creation of table/listing will appear bottom left under the sponsor name. The source listing number will appear bottom left.

Tables and listings will be produced in rich text format (i.e., they will tabular in format).

A landscape layout will be used for both tables and listing.

The left and right margins of all tables and listings will be a minimum of 2.1 cm from the left and 1.9 cm from the right. The top and bottom margins will be a minimum 2.92 cm. Header and footer will be both 1.27 cm.

A 9-point font size for tables and 7 or 8-point font size for listings will be used using Courier New font. A maximum SAS line size=141 and page size=44 for 8-point font size, and line size=161 and page size=50 for 7-point will be used so as to fit on both UK and US paper sizes.

A portrait layout will be used for figures.

Titles and footnote will not be included in the body of figure.

The size of the figures (except forest plot) will be: width=16.3 cm height=12.2 cm. The size of forest plot figures will be: width=16.3 cm height=20 cm. The resolution will be set using the option IMAGE_DPI=400.

All tables, listings and figures will be collated into three Microsoft Word complete documents. If the listings are too large to be included in one file they will be separated into manageable sized files. The Microsoft Word documents will be subsequently converted in PDF format. Both, Word and PDF documents will include a table of contents with hyperlinks.

13.4 Quality Control

The following steps will be taken to ensure the quality of the outputs:

- The author of each table/listing/figure program will review the program and will verify that no error message is highlighted in the 'LOG' file.
- Tables and figures will be independently programmed from the raw datasets by a second statistician/programmer and outputs will be compared either electronically (by comparing the data being tabulated using PROC COMPARE) or by manually comparing the data in the two independent outputs.

- Listings will be checked either electronically (by comparing the data being listed using PROC COMPARE) or by manually comparing the data in the listings to the raw/derived data.
- All outputs will be compared to the shells.
- Related outputs will be compared for consistency.

14 SAS Code

14.1 Tables that need descriptive statistics

```
PROC UNIVARIATE DATA=dset NOPRINT;  
  VAR var1 var2 var3 ...varn;  
  BY byvar; (optional)  
  OUTPUT OUT=outname  
  N=n MEAN=mean MIN=min MAX=max MEDIAN=median STD=std CV=cv;  
RUN;
```

Notes:

- var1, var2 represent the variables for which summary statistics will be calculated;
- byvar represents by variables to be used if any
- out=outname specifies the output dataset that should be created

For tables that need also geometric mean and geometric CV, the original variable will be LOG transformed and the geometric mean will be calculated using exp (mean_Log_var) and Geometric CV will be calculated using $\sqrt{\exp[\text{std_Log_var}^2]-1}$

14.2 Tables that need frequency counts

```
PROC FREQ DATA=dset NOPRINT;  
  BY byvar; (optional)  
  TABLES var1*var2; (for two ways table)  
  TABLES var1 var2; (for one way table)  
  OUTPUT OUT=outname;  
RUN;
```

Notes:

- byvar represents by variables to be used for frequency tabulations, if any
- var1, var2 represent the variables to be tabulated;

15 References

NA
